## **8 ASSESSMENT OF SAFETY**

### **8.1 Safety Parameters**

Safety assessments will consist of monitoring and recording adverse treatment events. Changes in clinical laboratory, clinical status and physical examination values will be used for evaluation.

To allow for the assessment of potential infusion toxicity at least 1 day will pass between the infusions of the Investigational Product/Placebo for each of the first five (5) subjects.

#### **8.1.1 Adverse Event (AE)**

ICH E6 defines an AE as any untoward medical occurrence in a subject or clinical investigation subject administered a pharmaceutical product regardless of its causal relationship to the study stem cell administration. An AE can therefore be any unfavorable and unintended sign (including an abnormal laboratory finding), symptom, or disease temporally associated with the use of medicinal (investigational) product. The occurrence of an AE may come to the attention of study personnel during study visits and interviews of a study recipient presenting for medical care, or upon review by a study monitor.

All AEs including local and systemic reactions not meeting the criteria for “serious adverse events” will be captured on the appropriate CRF. Information to be collected includes event description, time of onset, clinician’s assessment of severity, relationship to study product (assessed only by those with the training and authority to make a diagnosis) which would include MD, DO, PA or NP and time of resolution/stabilization of the event. All AEs occurring while on study must be documented appropriately regardless of relationship. All AEs will be followed to adequate resolution.

Any medical condition that is present at the time that the subject is screened will be considered as baseline and not reported as an AE. However, if it deteriorates at any time during the study, it should be recorded as an AE.

All AEs must be graded for severity and relationship to study product.

**Severity of Event:** All AEs will be assessed by the clinician using the following grading system of AE intensity.

- Mild: events require minimal or no treatment and do not interfere with the subject's daily activities.
- Moderate: events result in a low level of inconvenience or concern with the therapeutic measures. Moderate events may cause some interference with functioning.
- Severe: events interrupt a subject's usual daily activity and may require systemic drug therapy or other treatment. Severe events are usually incapacitating.
- Life threatening: any adverse drug experience that places the subject, in the view of the investigator, at immediate risk of death from the reaction as it occurred, i.e., it does not include a reaction that had it occurred in a more severe form, might have caused death.

Changes in the severity of an AE will be documented to allow an assessment of the duration of the event at each level of intensity to be performed. AEs characterized as intermittent require documentation of onset and duration of each episode.

**Relationship to Study Products:** The clinician's assessment of an AE's relationship to investigational product is part of the documentation process, but it is not a factor in determining what is or is not reported in the study. If there is any doubt as to whether a clinical observation is an AE, the event will be reported. All AEs must have their relationship to investigational product assessed. In a clinical trial, the investigational product must always be suspect. To help assess, the following guidelines are used.

- Related – There is a plausible temporal relationship between the onset of the AE and administration of the investigational product, and the AE cannot be readily explained by the subject's pre-existing clinical state,

intercurrent illness, or concomitant therapies; and/or the AE follows a known pattern of response to the investigational product; and/or the AE abates or resolves upon discontinuation of the investigational product and, if applicable, reappears upon re-challenge.

- Not Related – There is good evidence that the AE has an etiology other than the investigational product (e.g., pre-existing medical condition, underlying disease, intercurrent illness, or concomitant medication); and/or the AE has no plausible temporal relationship to administration of the investigational product (e.g., cancer diagnosed 2 days after treatment).

### **8.1.2 Serious Adverse Event (SAE)**

An SAE is an AE that results in any of the following outcomes:

- Death (i.e., the AE actually causes or leads to death)
- Life threatening event (i.e., the AE, in the view of the Investigator, places the subject at immediate risk of death)
- Requires or prolongs inpatient hospitalization
- Results in persistent or significant disability/incapacity (i.e., the AE results in substantial disruption of the subject's ability to conduct normal life functions)
- A congenital anomaly/birth defect in a neonate/infant born to a mother exposed to the investigational product(s)

Any other important medical event that may not result in death, be life threatening, or require hospitalization, may be considered a serious adverse experience when, based upon appropriate medical judgment, the event may jeopardize the subject and may require medical or surgical intervention to prevent one of the outcomes listed above. Examples of such medical events include allergic bronchospasm requiring intensive treatment in an emergency room or at home, blood dyscrasias or convulsions that do not result in inpatient hospitalization.

The terms “severe” and “serious” are not synonymous. Severity refers to the intensity of an AE (as in mild, moderate, or severe pain); the event itself may be of relatively minor medical significance (such as severe

headache). “Serious” is a regulatory definition and is based on subject or event outcome or action criteria usually associated with events that pose a threat to a subject’s life or vital functions. Seriousness (not severity) serves as the guide for defining regulatory reporting obligations.

Severity and seriousness will be independently assessed when recording AEs and SAEs on the CRF.

## **8.2 Methods and Timing for Assessing, Recording, and Analyzing Safety Parameters**

The Investigator is responsible for ensuring that all study-emergent AEs and SAEs are recorded on the CRF and reported to the sponsor in accordance with protocol instructions. For each SAE observed, the investigator will obtain all of the information available about the event, including (but not limited to): hospital discharge diagnoses, hospital discharge note, death certificate, appropriate laboratory findings (including autopsies and biopsy results), and clinical examinations (including radiological examinations and clinical consultations).

### **8.2.1 Adverse Event Reporting Period**

The study period during which all AEs and SAEs must be reported begins after initiation of study treatment and ends at study completion or study discontinuation/termination, whichever is earlier. Any condition present between consenting and time of treatment will be considered as baseline and not recorded as an AE. After this period, investigators should report only SAEs that are attributed to study treatment.

All AEs that are observed or reported prior to initiation of study treatment will be recorded as unrelated to treatment and those occurring after initiation of treatment will be recorded as treatment-emergent.

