## 4.2 Endpoints

### PRIMARY ENDPOINT

#### **Safety of MSCs assessed at the following time-intervals:**

Baseline and days 30, 60, 90, 180, and 360 post-initial infusion

1. Procedural complications
2. Vital signs
  - a. Temperature
  - b. Mean arterial blood pressure
  - c. Heart rate
  - d. Respiratory rate
  - e. Weight
  - f. LVAD parameters: Pump speed, flow, pulsatility and power
3. Uncontrolled systemic infection.
4. Hemodynamically unstable clinical arrhythmias that require appropriate defibrillator shock, anti-tachycardia pacing or initiation or escalation of antiarrhythmic medications.
5. Laboratory tests
  - a. Complete blood count (CBC)/ differential.
  - b. Comprehensive Metabolic Panel: Sodium, potassium, chloride, bicarbonate, blood urea nitrogen (BUN), creatinine, glucose, calcium, magnesium and liver function tests (ALT, AST, alkaline phosphatase, bilirubin and albumin)
  - c. Troponin-I.
  - d. Allosensitization (change in antibodies against HLA (panel reactive antibody test) from baseline for strong HLA antibody specificities (MFI>2000))
6. Electrocardiogram.
7. All-cause mortality. This will be reviewed by the DSMB. The LVAD population is a high risk group with very

high mortality, which will be taken into account when reviewing safety. Survival rate among HF patients with LVAD is 95% at 1 month, 81% at 1 year, 70% at 2 years, 59% at 3 years and 49% at 4 years. For patients enrolled within our study window, we would expect a 20% mortality rate in our patient population.

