## **5.2 Method of Treatment Assignment and Blinding**

This study is a Phase IIa, double-blind, placebo-controlled, multi-site (up to 2), randomized trial comprised of 30 subjects with an experimental group (stem cell infusion; n=15) and a placebo group (n=15; LRS at a volume of 1.5 mL/kg). Each group will receive 3 repeated doses of the assigned treatment (no cross-over) at times 0, 30 and 60 days. The infusion bags of stem cells or placebo will be identical.

In the event that a patient is unable to receive an infusion on or within the window of 30 or 60 days, the earliest infusion will be scheduled once it has been deemed safe for infusion. The primary endpoint measurement at day 90 (or within window) will remain irrespective to the number of infusions completed. More specifically, if infusion #2 (day 60) is missed then it will be scheduled as soon as the patient is deemed stable. The infusion #3 will occur 30 days from infusion # 2 but before day 90 (plus window) primary endpoint imaging evaluation. In the event that infusion # 3 would fall after the upper bound of the 90 day primary endpoint window then this infusion will be skipped.

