## **5.3 Subject Discontinuation and Withdrawal**

Subjects have the right to withdraw from the study at any time. Subjects will be given the option to provide a reason for withdrawal. In case of early withdrawal, the reason for withdrawal will be recorded on the appropriate Case report form (CRF). Attempts to complete early termination exam as defined in 7.4 will be made. The Investigator has the right to discontinue a subject from the study for any medical reason that the investigator determines may jeopardize the subject's safety if he or she continues in the study, or for reasons of noncompliance (e.g., missed visits, use of other investigational drugs, etc.).

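### Outcome follow-up is not secured after a subject is discontinued from the study, so later unattributed deaths and SAEs can be missing from the primary safety endpoint to Day 360

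*Combined protocol and SAP*

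**What the plan says.** **Endpoint.** Section 4.2 lists the safety items, all-cause mortality among them, as the primary endpoint, assessed at "Baseline and days 30, 60, 90, 180, and 360 post-initial infusion". Mortality there is all-cause, with no reference to attribution.

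**Leaving the study.** Section 5.3 states: "The Investigator has the right to discontinue a subject from the study for any medical reason". The sentence continues with a condition, namely that the investigator judges continued participation may endanger the subject, and adds noncompliance, with missed visits as an example. The only follow-up that section 5.3 names is this: "Attempts to complete early termination exam as defined in 7.4 will be made". The visit described in section 7.4 records admissions and AEs once. Unlike the Day 90, 180 and 360 visits in section 7.3, it does not list all-cause mortality, and no contact is scheduled after it.

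**Reporting period.** Under section 8.2.1 the period "ends at study completion or study discontinuation/termination, whichever is earlier". It adds: "After this period, investigators should report only SAEs that are attributed to study treatment".

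**Provisions that retain subjects or events.**
- Section 5.2 on missed infusions: "The primary endpoint measurement at day 90 (or within window) will remain irrespective to the number of infusions completed".
- The text on administration of the cells, under Subject Participation, keeps a subject whose infusion was stopped for a reaction on the visit schedule.
- Section 8.4 follows events still unresolved until they resolve or stabilize, the subject is lost to follow-up, or treatment and participation are judged not to be the cause.

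**Analysis.** The introduction to section 9 plans descriptive analysis of available data with no substitution for missing values, and tables that show how many subjects have complete data.

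**The concern.** An all-cause mortality endpoint to Day 360 needs every subject's vital status at Day 360. The plan has a route by which a subject leaves before then, and nothing after the exit exam would establish whether that subject is alive. On the subject-level reading of section 8.2.1, a later death is reportable only if the investigator attributes it to treatment. That sits badly with section 8.1.1, which says the assessed relationship to the product does not decide what gets reported. It also weakens two safeguards. Section 8.2.2 allows attribution to be revised as evidence accumulates, and section 8.5 has the sponsor send all SAEs to the DSMB. Neither can work on an event that was never reported.

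Discontinuation for a medical reason is likely to be related to prognosis. Missed visits may or may not be. With 15 subjects per arm and an available-data analysis, a few such exits, particularly if they are uneven between arms, could change the mortality count that the trial exists to describe. A later analysis plan cannot recover data that were not collected.

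**Working it through.** **1. The plan's own mortality figure.** Section 4.2 gives survival of 95% at 1 month and 81% at 1 year, and expects 20% mortality without naming a time horizon. From the survival figures, 1 − 0.81 = 19%, so the 20% is consistent with one year. Expected deaths per arm: 0.20 × 15 = 3.

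**2. Mortality after an early exit.** Assume a constant hazard between month 1 and month 12.
- Monthly hazard = ln(0.95 / 0.81) / 11 = 0.1594 / 11 = 0.0145.
- Day 60 to Day 360 is 300 days, or 300 / 365 × 12 = 9.86 months.
- Risk = 1 − exp(−0.0145 × 9.86) = 13.3%.

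The survival figures run from implantation, whereas the study clock starts at first infusion, so this is an approximation.

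**3. Later deaths among subjects who leave.** The documents give neither the number leaving, nor the timing, nor the prognosis. I assume exit at Day 60, 1 to 4 subjects in an arm, and a hazard 1 to 4 times the plan's. Expected later deaths = number leaving × [1 − exp(−HR × 0.0145 × 9.86)].

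| Leaving alive at Day 60 | HR 1 | HR 2 | HR 3 | HR 4 |
|---|---|---|---|---|
| 1 | 0.13 | 0.25 | 0.35 | 0.44 |
| 2 | 0.27 | 0.50 | 0.70 | 0.87 |
| 4 | 0.53 | 0.99 | 1.39 | 1.74 |

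Against 3 expected deaths, the bottom row runs from 0.53 / 3 = 18% to 1.74 / 3 = 58%. These are deaths at risk of being missed, not deaths certain to be missed. Any attributed to treatment stay reportable, and some arising from events open at exit would be picked up under section 8.4.

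**4. Bounds without a hazard assumption.** Suppose an arm records 3 deaths and 4 others were discontinued alive with no later vital status. True mortality then lies between 3/15 = 20% and 7/15 = 46.7%. A recorded 3 v 3 (two-sided Fisher p = 1.00) could be at most a true 7 v 3 (p = 0.245) if all four exits were in one arm. Neither would reach a conventional 0.05 (my assumption; the plan states no level). The harm is to the descriptive estimate rather than to a test decision.

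**5. Why up to four.** Section 5.4 lists 5 or more drop-outs per arm as a reason the sponsor may stop the study, so four does not meet that item. Section 5.4 also lists 20% or more missing primary safety data. Four exits in one arm is 4/30 = 13.3%, below it. Four in each arm is 8/30 = 26.7%, which could meet it.

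**The case against.** **The reporting clause may mean the trial.** The protocol uses study termination (section 5.4) and study completion (section 10.2) for the trial as a whole. On that reading, reporting does not close when one subject leaves. This stands as a real ambiguity. The subject-level reading is more natural: the period opens with study treatment, section 5.3 uses discontinuation for individuals, and section 7.4 uses early termination for an individual's visit. Even on the trial-level reading, no contact is planned through which a later death would be found.

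**Open events are followed.** This also stands. Section 8.4 would follow a deterioration still unresolved at exit, and a death from it may be captured. It does not cover new events, or events whose follow-up has already ended under that section.

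**Subjects who miss infusions are already retained.** A reader might infer that the plan contradicts itself, or that stopping infusions removes a subject. The documents do not support either. Sections 5.2 and the administration text set the default of staying in follow-up, and section 5.3 is a discretionary exception to it.

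**Mortality is a separate assessment.** A reader might infer that the endpoint turns into treatment-attributed mortality for these subjects. It does not: sections 4.2 and 7.3 record all-cause mortality independently of AE attribution. For discontinued subjects the endpoint is missing, not redefined.

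**The study is descriptive and unpowered.** True (sections 9 and 9.3); section 9.2 states Fisher's test for AE incidence, and the tables would show incomplete data. But showing the gap does not fill it, and in a descriptive safety study the counts are the result.

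**Conclusion.** The concern holds as a gap in ascertainment of the primary endpoint. After discontinuation from the study, the plan neither schedules vital-status follow-up to Day 360 nor, on the more natural reading of section 8.2.1, asks for SAEs not attributed to treatment. The exposure is limited to new unattributed events and deaths, and to events no longer followed under section 8.4.

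For four subjects leaving one arm at Day 60, about 0.5 later deaths are expected at the plan's own survival figures, set against about 3 expected in the arm. The 1.0 to 1.7 range requires an assumed hazard 2 to 4 times higher. The number leaving, the timing and the hazard ratios are all assumptions. Section 5.4 should not be read as accepting four drop-outs per arm, because its list of stopping reasons is expressly not exhaustive. A reader might also infer that the comparison will favour one arm. The documents do not show that exits would differ by arm; they show only that nothing would reveal the consequence if they did.

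**What to change.** Reconcile sections 4.2, 5.3 and 8.2.1:

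- **Section 8.2.1:** state that, for every infused subject who has not withdrawn consent for follow-up, deaths and SAEs are collected to Day 360 regardless of attribution and of discontinuation. Say explicitly whether discontinuation and termination refer to the subject or to the trial.
- **Section 5.3:** state that discontinuation by the investigator does not end outcome follow-up. Obtain vital status and hospitalisation at Days 90, 180 and 360 by visit, phone or chart, as consent allows. Record withdrawal of consent for follow-up as a separate status.

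The investigator's judgement on stopping infusions or study procedures stays as it is; the change concerns only what is collected afterwards. The cost is a short amendment, a line in the consent form, and a few calls or chart checks for what should be a small number of subjects.

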### **8.2.2 Assessment of Adverse Events**

Investigators will seek information on AEs and SAEs at each subject contact by specific questioning and, as appropriate, by examination. All AEs and SAEs, whether spontaneously reported by the subject or noted by authorized study personnel, will be recorded in the subject’s medical record and on the appropriate AE or SAE

CRF page.

Each recorded AE or SAE will be described by its duration (i.e., start and end dates), severity, regulatory seriousness criteria if applicable, suspected relationship to the investigational product, and actions taken.

Note: The investigator's assessment of causality for individual AE reports is part of the study documentation process. Regardless of the "Yes" or "No" causality assessment for individual AE reports, the sponsor will promptly evaluate all reported SAEs against cumulative product experience to identify and expeditiously communicate possible new safety findings to investigators and applicable regulatory authorities. Attribution of SAEs will be reviewed on an ongoing basis, and may be changed as additional clinical data emerge (e.g., reversibility of AE, new clinical findings in subject with AE, effects of retreatment, AEs in other subjects).

### 8.2.3 Recording Adverse Events on the CRF

Investigators will use correct medical terminology/concepts when recording AEs or SAEs on the CRF. Avoid colloquialisms and abbreviations.

AEs will be recorded either on an AE CRF page (if no serious criteria are met) or SAE CRF page, but not both. For each SAE observed, the investigator must report the triggering event for that particular episode of illness as the primary event.

Only one medical concept will be recorded in the event field on the AE or SAE CRF page.

### 8.3 Expedited Reporting Requirements for Serious Adverse Events

Any life-threatening (i.e., imminent risk of death) or fatal AE that is attributed by the investigator to the investigational product will be **telephoned to the Medical Monitor (or alternate) immediately**.

**Medical Monitor:** TBD

For initial SAE reports, investigators will record all case details that can be gathered within 24 hours on an SAE CRF page. The completed SAE CRF page will be faxed immediately upon completion to the attention of: [name], M.D., Ph.D., President and Chief Medical Office, Stemedica Cell Technologies, Inc

#### **8.4 Type and Duration of Follow-Up of Subjects After Adverse Events**

The Investigator will follow all unresolved study-emergent AEs and SAEs until the events are resolved, stabilized, the subject is lost to follow-up, or until it has been determined that the study treatment or participation is not the cause of the AE/SAE. Resolution of AEs and SAEs (with dates) will be documented on the appropriate AE or SAE CRF page and in the subject's medical record to facilitate source data verification.

For some SAEs, the sponsor or its designee may follow-up by telephone, fax, electronic mail, and/or a monitoring visit to obtain additional case details deemed necessary to appropriately evaluate the SAE report (e.g., hospital discharge summary, consultant report, or autopsy report).

#### **8.5 Data Safety and Monitoring Board (DSMB)**

An independent DSMB appointed by the Sponsor will review the protocol and will thereafter provide medical and ethical guidance related to the conduct of this trial. During the study, the board will conduct ongoing review of the nature, frequency and severity of safety data. The DSMB Chairperson has the option to recommend suspension of enrollment in the study if, upon initial deliberation by the DSMB, urgent safety issues or alarming trends in summary safety data are identified that require further investigation.

The study sponsor will report all SAEs to the study DSMB. The DSMB will determine whether enrollment will be

continued, suspended, or terminated. In the event that the DSMB determines that the study will be suspended or terminated, the study sponsor will notify the Institutional Review Boards and the appropriate regulatory agencies.

